4.1. Adequacy of protection against risks

We will administer an informed consent form both verbally and in writing to all participants in the local language for participation in all study activities. These forms will be read or will be given to participants to read themselves and will include a full description of voluntary participation, the right to withdraw from the study at any time, and the right to not answer any question or participate in any component of the research.

These forms will also address the risks, benefits, and purpose of the study and what we hope to learn, with a specific focus on the potential risks associated with the administration of SLD-PQ. We will train all interviewers extensively on the consent procedure, and each form will be co-signed by a team member to ensure all participants have consented. Checks in the field by the PI and project leaders will further ensure the consent process is followed in all cases. Data collection team members will provide the contact information for study coordinators who can be contacted for any further information on the topics brought up in the interview, or for additional treatment if necessary. The confidentiality procedures are designed to meet all contingencies to ensure the confidentiality of participant data and the privacy of the participants is preserved.

Our proposed strategies to reduce risks to privacy or of disclosure of confidential information include:

1. Identifying information will be recorded only in secure database software on password protected computers, and data collectors will only have access to the data that they themselves directly collect which will be cleared from their devices after all follow-up visits are completed. All data will be stored only in password-protected files on password-protected computers in locked offices.
2. Prior to analysis, data will be de-identified with the exception of geo-location codes, which are necessary for specific per-protocol analyses. The absence of individual identifying information will protect subject confidentiality.
3. All paper records will be stored in a locked location.

The potential risks of drawing blood from a finger-prick include temporary discomfort, pain, transient bleeding, bruising, skin infection, and fainting. The volumes of blood taken will be too small to produce any adverse physiologic effects from blood loss anemia and overall the aforementioned risks associated with blood draws are likely to be low. Study staff will be trained in the proper conduct of a finger-prick according to standard operating procedures to minimize the risk of discomfort and infection.

4.2. Protection against risks associated with administration of PQ

The main safety concern for primaquine administration is the risk of acute hemolytic anemia in individuals with glucose-6-phosphate dehydrogenase (G6PD) deficiency¹⁷. In a context where G6PD testing is not available, a dose of 0.25mg/kg of PQ has been found to be safe in individuals with any of the G6PD variants and is recommended by WHO¹³. All individuals RDT+ for *P. vivax* will be referred to and tested at a health facility using a G6PD Carestart RDT and a 14-day course of primaquine will only be given to G6PD non-deficient individuals. After the first six months, a subset of VMWs will conduct G6PD testing under supervision by a study staff member for *P. vivax* cases diagnosed in the community. Primaquine is typically well tolerated but possible side effects include nausea, headache, fatigue, dizziness, hives, chest pain, painless darkening of urine, jaundice of skin, vomiting and syncope (fainting). In line with national guidelines, PQ will not be administered to pregnant women in any trimester or to women unable to undergo pregnancy testing, children less than 6 months of age, infants weighing less than 10 kg, women in the first 6 months of breastfeeding, or individuals with prior allergic reaction to PQ or related drugs.

The key to managing side effects and any potential adverse events (AEs) or serious AEs (SAEs) is thorough training of VMWs/VHVs, health facility staff and supervisors, and intensive sensitization of the community. HC workers and VMWs/VHVs will passively monitor their respective communities for AEs and refer any potential SAEs to designated health facilities. Health workers at these facilities will be informed of the project and potential side effects, and undergo training on completion of AE reporting forms (8.14 and 8.15). Cases that cannot be treated at health centers will be referred to district or provincial hospitals.

All participants receiving study drug will be provided with an informational sheet listing potential side effects and instruction to seek care at the nearest health center should they experience any of the defined symptoms or other adverse events. Community sensitization events and targeted IEC/BCC materials will also help increase community awareness of potential adverse events and encourage early care-seeking if events arise.

A passive case detection system will be employed in both intervention and control villages to help detect and refer any potential SAEs and active follow-ups will be conducted by VMWs on days 3, 7, and 14; VMWs/VHVs will be oriented on potential drug side effects and asked in addition to passively monitor their communities and refer any potentially serious or unexpected AEs. All public health facilities in the nine target districts will be trained on AE reporting procedures prior to implementation of any study activities. A data safety monitoring board (DSMB) will be established to oversee and report on any SAEs that are potentially linked to the administration of AL or SLD-PQ, as outlined in further detail in Section 4.5. The following steps will be taken for all AEs:

The health facility will complete an AE reporting form (Appendix 8.14). The completed form will then be submitted to the Local Safety Monitor (a medical doctor), who with the support of the UCSF project manager will assess if the event is an SAE or unexpected AE based upon specific criteria determined by the DSMB. If determined to be an SAE or unexpected AE, the UCSF project manager will submit the AE reporting form and any accompanying documentation (clinical records, laboratory reports) to the DSMB and the UCSF PI within 48 hours from the identification of the potential SAE.

Upon receipt of the AE reporting form, the DSMB will complete an AE investigation form (Appendix 8.14) within 24 hours to a) confirm if the event is an SAE, and 2) to determine if the SAE was caused by the administration of AL with SLD-PQ as part of this study. If the event is confirmed to meet the criteria of an SAE, the DSMB will submit the completed AE investigation form to the PI, who will submit to the research ethics committees (RECs) at UCSF and NIOPH. The respective RECs will be notified within 24 hours of the DSMB's completion of all potential SAE investigation forms, and within 48 hours of DSMB notification if deemed an AE, but not fulfilling criteria for an SAE.

Travel and hospitalization costs for any SAEs resulting from PQ administration will be covered by the study.

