All individuals who test positive by either HS-RDT or Standard RDT will be told of their results and treated on site per national guidelines:

- Individuals with *P. falciparum* infection will be treated with an age-appropriate course of artemether-lumefantrine (AL) and a single low dose of primaquine (SLD-PQ). Weight-based dosing is described in Tables 2 and 3 below.
- At all study sites in Lao PDR, patients with a *P. vivax* infection identified by RDT (both febrile and asymptomatic) will be given a unique coded and signed informational letter directing them to the nearest district hospital (or other testing facility) for G6PD deficiency testing and possible radical cure administration depending on results. Study contact information will also be included if the participants present at other health facilities. At the health facility, G6PD normal individuals will be treated with AL and a 14-day course of PQ, whereas G6PD deficient individuals will receive AL alone as per the national guidelines and referred to a hospital for further primaquine management decisions. The study staff will meet with district hospital and health facility staff monthly from all study areas and nearby district hospitals and health facilities to collect these forms, with small incentives for health staff to report receiving a study card (phone top up card, etc.) to maximize data completeness. After six months of implementation, a subset of VMWs will begin conducting qualitative G6PD testing and treatment administration at the community-level with the assistance of a health facility staff member.

Table 2. AL weight-based dosing

Body weight (kg)	Tablet strength (mg)		Tablets/dose	Mg of drug per dose		Tablets/day
	Artemether	Lumefantrine		Artemether	Lumefantrine	
5 to 14	20	120	1	20	120	1 tablet given twice* per day for 3 consecutive days

15 to 24	20	120	2	40	240	2 tablets given twice* per day for 3 consecutive days
25 to 34	20	120	3	60	360	3 tablets given twice* per day for 3 consecutive days
35 or greater	20	120	4	80	480	4 tablets given twice* per day for 3 consecutive days
*Approx. 8 hours between doses 1 and 2. Approx. 12 hours between all other consecutive doses.						

Table 3. Weight-based dosing of SLD- Primaquine (.25 mg/kg) for *P. falciparum*

Body weight (kg)	SLD-PQ dose (7.5 mg tablet) (as base)	Tablets
10 to < 25	3.75	1/2
25 to < 50	7.5	1
50 to 100	15	2
*Given as SLD in addition to AL for P falciparum positive		

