Table 4. Age-based dosing of Primaquine for *P. vivax*

Items	Dose	No. of tablet/day	Frequency	Duration
G6PD Normal				
Children				
4-8 years old	5 mg/day	1/3	Once per day after meal	14 days
9-14 years old	10 mg/ day	2/3		
>14 years old (adults)	15 mg/ day	1		

Per national guidelines in Laos, AL will not be given to women who are pregnant or may be in their first trimester. All women of reproductive age with a last menstrual period greater than four weeks positive HS RDT or Standard RDT will be offered a pregnancy test. Pregnancy testing and consent will be embedded in the participant questionnaire. Any woman who acknowledges pregnancy in the first trimester or confirmed by a positive pregnancy test or refuses to take a pregnancy test will be excluded from receiving AL and will be referred to the nearest health facilities for treatment.

Contraindications to primaquine include pregnancy (any trimester), age less than 12 months, infants weighing less than 10 kilograms, women in the first 12 months of breastfeeding, and prior allergic reaction to primaquine. Participants with contraindications to primaquine will not be excluded from the study and will receive first-line treatment alone, provided they are eligible.

All individuals with suspected severe malaria or other severe illness (including those with symptoms of severe anemia, prostration, impaired consciousness, respiratory distress, convulsions, circulatory collapse, abnormal bleeding, jaundice or passing dark urine) will be referred to the nearest health facility for clinical assessment and treatment.

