3.3.2. Adherence and safety monitoring

To ensure participants' adherence to their medication and monitor safety, participants will be informed on how to take their medications, about the side effects of the treatment and the importance of compliance to the treatment. In addition to DOT on day 0, The VMW will conduct a day

3, day 7, and day 14 adherence and safety monitoring visit for all individuals treated with primaquine for *P. vivax*, and the VMW will ask a series of questions to determine adherence with each dose, number of remaining tablets, potential adverse events, and reasons for non-adherence or treatment refusal. Participants with phone number will be sent a daily text message to remind them to adhere to their treatment and remind them about any symptoms suggesting serious adverse events. All participants and their family members will be provided a chart to record and track their adherence as well as symptoms that may indicate an adverse event.

The safety risks associated with participation in this trial are expected to be minimal. The study drugs, AL and PQ, are well tolerated first-line treatments and safe for G6PD non-deficient individuals. Prior to drug administration, participants will be asked about known contraindications, and if such contraindications are reported, participants will be restricted from taking the medication.

Drug	Contraindications
AL	Pregnancy, infants < 5kg, prior allergic reaction, any severe disease
PQ	Pregnancy, age < 12months, infants < 10kg, women in first 12 months of breastfeeding, prior allergic reaction, any severe disease, G6PD deficient

The common adverse events reported for each drug are as below:

- AL: headache, dizziness, loss of appetite, generalized weakness, fever, chills, arthralgia, myalgia, nausea, vomiting, and abdominal pain
- PQ: nausea, headache, fatigue, dizziness, hives, chest pain, painless darkening of urine, jaundice of skin and vomiting.

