4.6.2. Inclusion of vulnerable subjects – children and pregnant women

All age groups will be included in this study, except for those < 18 months. All children that participate must have the consent of the parent or guardian. Children older than 6 years and less than 18 must also provide oral assent before participation. All women who are pregnant or believe they may be pregnant will be assessed appropriately before treatment.

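### Primaquine is withheld until 12 months of breastfeeding in Protocol 3.3.1 and 3.3.2 but only until 6 months in 4.2 (minor)

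*Protocol*

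**What the plan says.** Three places in the protocol list who should not receive primaquine.

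- Section 3.3.1, under Case Management and Follow-up, gives "Contraindications to primaquine include pregnancy (any trimester), age less than 12 months, infants weighing less than 10 kilograms", and then "women in the first 12 months of breastfeeding, and prior allergic reaction to primaquine".
- The contraindication table in 3.3.2 has, in its PQ row, "Pregnancy, age < 12months, infants < 10kg, women in first 12 months of breastfeeding", followed by prior allergy, severe disease and G6PD deficiency.
- Section 4.2 withholds PQ from pregnant women, women who cannot be pregnancy-tested, "children less than 6 months of age, infants weighing less than 10 kg", and "women in the first 6 months of breastfeeding, or individuals with prior allergic reaction to PQ or related drugs". It describes this list as following national guidelines.

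On safety oversight, 4.2 sets up a DSMB to "oversee and report on any SAEs that are potentially linked to the administration of AL or SLD-PQ". It then asks the DSMB to decide whether a serious adverse event (SAE) was caused by AL with SLD-PQ. The stopping-rule introduction in 4.5 also names AL plus SLD-PQ. Under 3.3.1, however, a G6PD-normal *P. vivax* patient receives AL and a 14-day primaquine course.

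**The concern.** A contraindication list should have one answer for each patient. A woman who has been breastfeeding for between 6 and 12 months is excluded from primaquine under 3.3.1 and 3.3.2 but is not on the exclusion list in 4.2. That section is the one devoted to protecting participants from primaquine risk, so staff, trainers or an ethics committee could reasonably consult it first and take 6 months as the rule. Treatment is partly in the hands of village malaria workers, and after six months a subset of them begins G6PD testing and treatment administration in the community. An unambiguous list matters in that setting.

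The DSMB wording raises a smaller question of the same kind. Section 2.6 describes SLD-PQ as safe with any G6PD variant, and 5.1 attaches the misclassification risk to 14 days of primaquine. The causality question in 4.2 names the first regimen and not the second.

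**Working it through.** No sample size, power or error-rate figure is involved, so the check is a comparison of the texts.

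**Breastfeeding limit**

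| Place | PQ withheld during breastfeeding | Guideline cited for the list itself |
|---|---|---|
| 3.3.1, Case Management and Follow-up | first 12 months | none in that sentence |
| 3.3.2, contraindication table | first 12 months | none |
| 4.2 | first 6 months | national guidelines |

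Width of the disputed interval: 12 − 6 = 6 months. The document gives no number of breastfeeding women, so a count of those affected cannot be derived.

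*Does another rule settle it?* The 10 kg floor and the study's minimum age act on the person treated and do not touch a breastfeeding adult. The pregnancy rules do not apply to her either, unless she is pregnant or cannot be tested.

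*Does the regimen explain it?* In 3.3.1 the contraindication sentence comes after the dosing tables for both regimens and speaks of primaquine in general. Section 4.2 discusses the single low dose and the 14-day course and then gives one list for PQ. Neither breastfeeding limit is assigned to a regimen.

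**Minimum age**

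The limit is 12 months in 3.3.1 and 3.3.2 and 6 months in 4.2. Section 4.6.2 states: "All age groups will be included in this study, except for those < 18 months". The disputed range, 6 to under 12 months, lies wholly below 18 months, so no participant falls in it. All three lists also keep the 10 kg floor.

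**DSMB wording**

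Three places name SLD-PQ and not the 14-day course: the remit in 4.2, the causality question in 4.2, and the stopping-rule introduction in 4.5. Against these stand texts with no such limit:

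- 3.3.2 sends SAEs and unexpected serious reactions to the DSMB through the principal investigator, and has the Local Safety Monitor determine causality.
- 4.5 has the DSMB consider adverse events from the drugs used in the study. Its stopping rules extend to possible drug-related hospitalisation, any other SAE, and a death attributed to any study drug.
- 4.5 also has the Local Safety Monitor review every SAE, give an opinion on causality and report back to the DSMB.

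A serious event on the 14-day course would therefore reach the DSMB. Only the wording of the causality question, with the matching remit and introduction, does not fit that patient's regimen.

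**The case against.** The best defence is that the lists in 3.3 and 4.2 state exclusions, and exclusions accumulate. Section 4.2 says who will not get primaquine; it authorises nobody. It is also not a complete list, since it omits the severe-disease exclusion found in the 3.3.2 table. Section 3.3.2 has participants asked about contraindications before dosing and restricts those who report one. Someone following the dosing sections reaches 12 months, stated twice. This defence largely stands and sets the severity. It does not remove the discrepancy, because nothing in the protocol says that 3.3 prevails over 4.2.

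A reader might infer that women at 6 to 12 months would be given primaquine under 4.2. The text does not go that far: absence from one exclusion list is not an instruction to treat.

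A reader might also argue that both limits claim the same authority, so one must misstate the guideline. Section 3.3.1 does say that people testing positive "will be told of their results and treated on site per national guidelines", but that phrase governs treatment in general. The 12-month sentence and the 3.3.2 table cite no guideline, and a protocol may be stricter than one. The guideline itself is not among the documents.

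A regimen-based defence has some footing: the PQ row in 3.3.2 includes G6PD deficiency, which suits only the 14-day course, because the single low dose is given without G6PD testing. That suggests the table's author had the longer course in mind, but it does not assign the 6-month limit in 4.2 to the single dose.

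On the DSMB, the defence is that 4.2 refers to 4.5 for detail and 4.5 is broad. That stands, and leaves a wording point only.

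**Conclusion.** The inconsistency is real and minor. Sections 3.3.1 and 3.3.2 give 12 months, 4.2 gives 6, and the protocol has two answers for a woman in the 6 months between. The operative dosing sections carry the safer limit, so likely harm is limited. Which limit is correct cannot be decided from the document. The age mismatch in the same lists has no practical effect, on the assumption that the 18-month minimum in 4.6.2 is applied throughout.

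The DSMB wording is a secondary slip. It might be read as leaving the 14-day course without safety oversight, but 3.3.2 and 4.5 show otherwise. It is also uncertain whether the investigation form repeats the narrow question, because the appendix forms are not shown.

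No outcome, power calculation or analysis is affected. The point deserves correction because it concerns a drug contraindication and costs almost nothing to settle.

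**What to change.** 1. State one breastfeeding limit in 3.3.1, 3.3.2 and 4.2. Use 12 months unless the national guideline specifies otherwise; the sponsor should check the guideline and say whether the protocol follows it or is deliberately stricter.
2. Align the minimum age in the same three lists.
3. In the DSMB remit and causality question in 4.2, and the stopping-rule introduction in 4.5, refer to AL or any primaquine regimen, including the 14-day course. Carry this into the investigation form if it repeats the question.

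The cost is wording in one protocol amendment. No extra visits, staff or data are needed.

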4.3. Potential benefits of the proposed research to the participants and others

The proposed research may benefit patients in direct and indirect ways. Participants will directly benefit from detection of low-level parasitemia, and the curative effects of AL administration on existing malaria infections in the RACD intervention arm. Furthermore, patients may directly benefit due to community-wide reductions in malaria transmission that are expected to occur after the application of the interventions. Finally, entire target village populations will benefit from SLD-PQ, which targets the parasite sexual stages thereby decreasing overall transmission.

Participants may also indirectly benefit, as the information gained from this research will be used to help establish the safety and efficacy of new malaria control interventions in both countries. The research will benefit the scientific and malaria control communities more generally by expanding the evidence base on RACD targeting high risk populations.

4.4. Alternatives to participation

Participation in the research study is voluntary. Individuals electing not to participate in the research study may still receive testing and treatment as part of the routine malaria case management. Individuals who do not wish to receive testing and treatment or presumptive treatment during the intervention campaigns may visit local health facilities for malaria testing and treatment.

4.5. Data and safety monitoring plan

The project will follow US National Institutes of Health (NIH) guidelines for establishing a data safety monitoring board (DSMB). The DSMB will be established prior to any data collection as part of this study. The members of the DSMB will serve in an individual capacity and provide their expertise and recommendations. The primary responsibilities of the DSMB will be to periodically review and evaluate the accumulated study data for participant safety, study conduct and progress, and, when appropriate make recommendations to investigators concerning the continuation, modification, or termination of the trial. DSMB will consider study-specific data as well as relevant background knowledge about malaria, adverse events from drugs used in the study, drug resistance, and the participant population under study.

Membership of the DSMB will consist of five independent experts in malaria control, diagnosis, case management and epidemiology, and one member of the research team to advise and clarify study activities for the independent experts. No independent member of the DSMB shall have any conflict of interest with the study team, the organizations funding or conducting the research, or the results of the study. The DSMB will be comprised of experts in the following areas, with an emphasis on local Lao expert participation:

- The study population in Lao PDR (Lao representatives)
- Malaria diagnosis and case management
- Malaria epidemiology
- Biostatistics
- Conduct of clinical trials
- Malaria drug resistance

No data on futility or benefit of the intervention will be estimable during the course of the trial as the timing of outcome data collection precludes developing stopping rules based on outcome data collected during implementation. Safety concerns associated with the wide-scale use of AL + SLD-PQ, although unexpected, will form the basis of development of a stopping rule. The stopping rules

for this trial will be based on detection of a significantly higher rate of mortality, hospitalization for possible drug-related events, or any other SAE in the intervention villages versus rates recorded at health facilities for the control villages. Further, any investigated SAE that results in death that is found to be due to the administration of one of the study drugs will be grounds for stoppage.

The Local Safety Monitor (physician) will review all SAEs, hospital admissions and deaths in the study areas, give an opinion on causality, and give regular feedback to the DSMB.

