Activity 3: Assessment of the operational feasibility and safety of conducting G6PD testing, referral, and treatment adherence among positive P. vivax RDT cases	1. Assess the operational feasibility of G6PD referral at community level	Proportion of VMWs who rate conducting G6PD referral as very easy, somewhat easy, somewhat difficult, and very difficult, and changes in proportions over time	Entrance, mid-intervention, and exit competency checklists with VMWs; focus group discussion and interviews with VMWs at end-line	
		Proportion of P. vivax cases with valid recorded G6PD result	VMW and health facility records	
	2. Determine risk factors for non-attendance at hospitals or health centers after referral for G6PD testing	Proportion of referred cases presenting at hospitals or health centers for G6PD testing.	Cross-sectional survey and qualitative studies at endline with villagers, forest workers, VMWs	
	3. Assess treatment adherence among positive P. vivax RDT cases	Proportion of patients with physical evidence of full adherence with the prescribed drug regimen	VMW follow-up visits on day 3, 7, and 14	
		Proportion of P. vivax cases who relapsed in the six months following treatment	VMW and health facility records	
	4. Assess the safety of community-level G6PD testing, referral, and P. vivax treatment follow-up	Adverse event rate per treated individual	RACD intervention data and VMW follow-up visits; health facility adverse event reporting forms	
	Activity 4: Assessment of the risk of malaria vector biting in forest and village settings	1. Describe local vector species composition and bionomics in forest and village settings	Vector occurrence and density by species; vector biting behaviors; human behavioral observations in relation to human biting rate (HBR)	Human Landing Catches (HLCs) vector sampling at baseline

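### Section 4.5's only rate-based safety trigger compares whole villages although RACD gives drug only to test-positives, so non-fatal drug harm is judged on the wrong denominator

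*Protocol*

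**What the plan says.** Section 4.5 sets two stopping grounds.

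- **Rate ground:** stopping is "based on detection of a significantly higher rate of mortality, hospitalization for possible drug-related events, or any other SAE in the intervention villages". The comparator is the control arm's village rates, as captured by its health facilities.
- **Individual ground:** stopping follows "any investigated SAE that results in death that is found to be due to the administration of one of the study drugs".

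Section 4.5 also lets the DSMB recommend modifying or ending the trial. Sections 4.2 and 4.5 give each SAE an individual causality review. The same section frames the hazard as "Safety concerns associated with the wide-scale use of AL + SLD-PQ", and section 4.3 states that "entire target village populations will benefit from SLD-PQ".

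The treatment rule is narrower. Section 3.3.1 (Case Management and Follow-up) says: "All individuals who test positive by either HS-RDT or Standard RDT will be told of their results and treated on site per national guidelines". The overview table in section 3.4.1 (Activity 3, objective 4) defines the safety outcome as "Adverse event rate per treated individual".

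**The concern.** The language of sections 4.3 and 4.5 fits a design in which whole villages take drug. In this trial nearly everyone in an intervention village takes none. A comparison of village-wide rates then asks whether two large, mostly untreated populations have similar SAE rates. It does not ask whether the drugs harm those who receive them. Dilution remains even if events are ascertained identically in both arms.

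What is at stake is non-fatal harm. Section 4.2 names acute haemolysis as the main primaquine concern, and the safety of community-level primaquine is a secondary objective. If serious non-fatal events rose among treated people, the one numerical trigger in the plan would be poorly placed to show it. A non-significant village comparison could also later be mistaken for reassurance.

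**Working it through.** **Inputs from the protocol**

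- Tested in RACD (section 3.4.2.4.3): 720 cases × (5 households × 4 people + 4 forest workers) = 720 × 24 = 17,280. This reproduces the stated figure.
- Population per arm: 60,000 (summary, 120,000 / 2), 64,000 (section 3.4.2.4.1, 16 × 4,000) or 73,899 (Table 1, 147,798 / 2).
- Smaller case count from section 3.4.2.4.1: 2.5 per 1,000 × 64,000 × 1.5 years = 240 cases, so 240 × 24 = 5,760 tested.
- Reference for serious haematocrit drops (section 2): 1 in 889 followed up.

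**Assumptions, because the protocol gives no figure**

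- Test positivity in RACD is 0.2% (PCR, the earlier Thai RACD study in section 2) to 2.5% (qPCR planning prevalence, section 3.4.2.4.2).
- All 720 (or 240) cases arise in the intervention arm.
- Drug-related SAE risk is 1% per treated person, unless stated otherwise.
- The test is one-sided 2.5%, one look, no clustering (favourable to the rule).

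**Step 1: exposed share**

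- 17,280 × 0.2% ≈ 35 people; 17,280 × 2.5% = 432 people.
- 432 is 0.58% of 73,899, 0.68% of 64,000 and 0.72% of 60,000.
- The share reaches 1% only at a positivity of 0.01 × 60,000 / 17,280 = 3.5%, or 0.01 × 73,899 / 17,280 = 4.3%.

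**Step 2: all-cause components**

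Excess events = 432 × 1% = 4.32. Background events per arm = rate × 64,000 × 1.5. Power comes from the exact conditional binomial test on two Poisson counts.

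| Assumed background per 1,000 person-years | Background events per arm | Power, 4.32 excess events |
|---|---|---|
| 1 | 96 | 4.3% |
| 5 | 480 | 3.2% |

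Both are close to the 2.5% false-positive rate.

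**Step 3: drug-related hospitalisation**

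Untreated villagers scarcely contribute here. The limits are small numbers and the treatment of index cases in both arms. Expected events are (index + extra) × risk in the intervention arm and index × risk × relative exposure in control.

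| Index cases / extra treated | Risk | Control exposure | Expected events | Power |
|---|---|---|---|---|
| 240 / 12 | 1% | equal | 2.52 v 2.40 | 0.5% |
| 240 / 144 | 1% | equal | 3.84 v 2.40 | 2.8% |
| 720 / 432 | 1% | equal | 11.52 v 7.20 | 11.6% |
| 720 / 432 | 1% | half | 11.52 v 3.60 | 45% |
| 720 / 432 | 1% | quarter | 11.52 v 1.80 | 73% |
| 720 / 432 | 2% | equal | 23.04 v 14.40 | 24% |
| 720 / 432 | 5% | equal | 57.6 v 36.0 | 57% |

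With no control events at all, significance needs at least 6 intervention events (0.5^6 = 0.016, against 0.5^5 = 0.031). A Poisson mean of 4.32 reaches 6 or more with probability 27%, and a mean of 1.44 with probability 0.4%.

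**Step 4: the same harm counted per treated person**

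This is an exact binomial test against 1/889 at one-sided 5%, one look, with a true risk of 1%.

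- 384 treated (240 + 144): critical count 3, power 74%.
- 432 treated: critical count 3, power 81%.
- 1,152 treated (720 + 432): critical count 4, power over 99%.

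For 384 and 432 treated the critical count of 3 also satisfies one-sided 2.5% (tail probabilities 0.0097 and 0.013), so the contrast with step 2 does not come from a looser alpha. Cumulative looks would lower these figures somewhat.

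**The case against.** The strongest reply is that the village comparison is not the only safeguard. A drug-caused death is its own ground for stopping, each SAE is reviewed for causality, and the DSMB may recommend termination. Section 5.2 foresees that an SAE from primaquine in a G6PD-deficient person could stop the study. This stands. A reader might infer from the rate rule that the trial simply continues unless village rates differ significantly. The protocol does not say that.

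A reader might also infer that the rule misses a relevant harm about nine times in ten. The documents do not support a single figure, because they state no alpha, background rate, harm size or RACD positivity. Control-arm exposure is unclear too. Section 2.1 says primaquine treatment is not yet widely in use, and Table 5 lists 14-day PQ only for the RACD arm, while section 3.3.1 refers to all study sites. Step 3 shows how far this moves the result. Positivity above 2.5% is also possible, since section 2 expects targeting of high-risk groups to find more infections.

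Two further points are fair. Nothing in the protocol claims that non-significance shows safety. And active follow-up of treated *P. vivax* patients, set against facility-recorded control rates, could trip the rule falsely rather than leave it silent. That would be a further fault, not evidence that the rule measures drug harm.

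Finally, section 4.5 speaks of a rule still to be developed, and alpha and looks may properly sit in a DSMB charter. But the comparison and its denominator are already written down, and those are what is at issue. The safeguards on individual events carry no stated threshold for non-fatal harm.

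**Conclusion.** The point holds in a limited form. The only pre-set rate trigger for non-fatal drug harm uses village populations as its denominator, although under 1% of an arm is treated through RACD unless positivity exceeds roughly 3.5% to 4.3%. It also differs from the trial's own per-treated safety outcome. For the all-cause components the dilution is severe: about 3% to 4% power for a 1% risk in 432 extra treated, given an assumed background of 1 to 5 per 1,000 person-years. For drug-related hospitalisation no one figure can be defended. The range runs from 0.5% to over 50%, and the cause is small numbers and index cases treated in both arms more than dilution. Fatal drug-related events are covered separately. This is a moderate design fault that should be corrected, and it does not show that the trial lacks safety oversight.

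**What to change.** In section 4.5, base the rate trigger on drug-related SAEs per person given study drug, counted separately for SLD-PQ and 14-day PQ. Monitor it cumulatively with an exact confidence bound against a maximum rate that the DSMB sets in advance; the value is for the DSMB. Keep the drug-caused-death ground and the DSMB's discretion as they are. Keep the between-village comparison as descriptive, and state that a non-significant result there is not evidence of safety.

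Report the final safety result as the per-treated rate with its upper bound. With no events, the one-sided 95% bound is 1 − 0.05^(1/n), which is 2.1% for 144 treated and 0.7% for 432. Reconcile the mass-treatment wording in sections 4.3 and 4.5 with treatment of test-positives only.

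The cost is a wording change to the protocol and the DSMB charter. The PROMPT forms, follow-up visits and AE forms already supply the counts. The downsides are that the DSMB must name an acceptable rate beforehand, and that the safety evidence is shown to be less precise.
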